5.13.6.2. Eosinophilia and Eosinophil-Related Disorders

In addition to the standard laboratory summaries (Section 5.13.3), eosinophilia and eosinophil-related AEs will be summarized. Details regarding- eosinophil-related PTs are in the compound-level safety standards.

Table KGBP.5.9. Summary Tables Related to Eosinophilia and Eosinophil-Related Adverse Events

Summaries	Population
Shift table summarizing the number and percentage of participants within each maximum baseline category versus each maximum postbaseline category	Safety

Summary of eosinophil-related TEAE by PT	Safety
--	--------

Abbreviations: AE = adverse event; PT = Preferred Term; TEAE = treatment-emergent adverse event.

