Visit Interval Tolerance (Days)		—	±3	±3	±5	±5	±5	±5	±5	—	±7		
Visit Detail						T		T					
PROs (Electronic)													
Complete prior to any clinical administered assessments													
PO-SCORAD		X					X		X	X			
DLQI		X					X		X	X		Only for participants ≥16 years of age at baseline.	
cDLQI		X					X		X	X		Only for participants <16 years of age at baseline.	
WPAI-AD		X					X		X	X			
ADCT		X		X			X		X	X			
Participant-Reported Satisfaction Question							X		X	X			
Clinician-Administered Assessments (Electronic)													
IGA	X	X	X	X	X		X		X	X			
F-IGA		X	X	X	X		X		X	X			
EASI	X	X	X	X	X		X		X	X			
BSA	X	X	X	X	X		X		X	X			
PDS		X					X		X	X			
Clinician-Administered Assessments (Paper)													
Fitzpatrick Skin Type Assessment	X												

	Period I	Period II									Period III	Comments	
	Screening	Baseline	Treatment Period									Post-treatment Follow-Up	
Visit Number	1	2	3	4	5	6	7	8	9	ED	801		
Week Relative to Study Drug Start	≤30 (days)	0	2	4	8	12	16	20	24	—	12 weeks post last dose		
Visit Interval Tolerance (Days)		—	±3	±3	±5	±5	±5	±5	±5	—	±7		
Visit Detail						T		T					
Participant Education and Supplies													
Participant or caregiver instructions on diary completion	X											Education can also be performed on an as-needed basis.	
Remind participant of TCS usage restrictions and expectations	X											Required 2-week wash out of TCS prior to Visit 2. See Sections 6.8.1, 6.8.2, and 6.8.5 for TCS usage.	
Train participant and/or caregiver on study intervention administration			X	X								Participants and/or caregivers need to be adequately trained on injection technique prior to administering injections. Training can be done at Week 2 and/or Week 4 prior to self-administration.	
Dispense ancillary supplies				X	X		X						
Laboratory Tests and Sample Collections													
Hematology	X	X		X			X		X	X	X		
Clinical chemistry	X	X					X		X	X	X		
Serum pregnancy	X											Only for WOCBP. Pregnancy tests prior to first dose of study intervention for females ≥12 years of age if menarche reached or if there is reason to believe the participant is sexually active. Pregnancy test results from baseline must be known prior to first dose of study intervention. See Section 10.4, Appendix 4.	

	Period I	Period II									Period III	Comments	
	Screening	Baseline	Treatment Period									Post-treatment Follow-Up	
Visit Number	1	2	3	4	5	6	7	8	9	ED	801		

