5.1.2 General Considerations for Analyses

All analyses will be descriptive. Frequencies, percentages, and 90% Wilson-Score CIs for percentages will be reported for discrete efficacy endpoints. Mean, standard deviation, minimum, Q1, median, Q3, maximum, and the number of participants will be reported for continuous

efficacy endpoints. AEs, discontinuation, and other categorical safety data will be summarized using frequencies and percentages. Continuous vital signs, body weight, and other continuous safety variables including laboratory variables will be summarized descriptively as well.

Baseline

Baseline will be defined as the last available value before the first injection for efficacy and health outcome analyses. In most cases, this will be the measure recorded at the baseline visit (Day 1). If the patient does not take any injection, the last available value on or prior to treatment assignment date will be used. Change from baseline will be calculated as the visit value of interest minus the baseline value.

For Pruritus Numeric Rating Scale (NRS), Skin Pain NRS, and Sleep-Loss due to Pruritus collected via eDiary, the baseline period is the 7-day window prior to the first injection. A patient must have responses on at least 4 of 7 days to calculate a baseline weekly mean. If a patient has 3 or fewer responses, the baseline mean value will be considered missing.

For the safety analyses, the following baselines will be used. For safety analyses using a baseline period, the baseline period is defined as the time from the screening visit to the date/time of the first injection.

- TEAEs: baseline will be all results recorded during the baseline period.
- Treatment-emergent abnormal laboratory and vital signs results: baseline will be all results recorded during the baseline period.
- Change from baseline to last post-baseline observation or to each scheduled postbaseline visit for laboratory and vital signs results: baseline will be the last scheduled non-missing assessment recorded during the baseline period.

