5.13.3. Clinical Laboratory Evaluation

As described more fully in compound-level safety standards and in the laboratory-related PhUSE white papers (PhUSE 2013; PhUSE 2015), the clinical laboratory evaluations will be summarized as described in [Table KGBP.5.6](#). Hormone analytes are summarized/Plotted similarly.

Table KGBP.5.6. Summary Tables/Listing of Clinical Laboratory Evaluations

Summaries	Population
Box plots of observed values by visit	Safety
Box plots for change from baseline values by visit	
Change from baseline to last observations	Safety
Treatment-emergent abnormal high lab values (ie, patients shifting from a normal/low maximum baseline value to a high maximum postbaseline value) or abnormal low lab values (ie, patients shifting from normal/high minimum baseline value to a low minimum postbaseline value)	Safety
Shift tables showing the number of patients who shift from each category of maximum (minimum) baseline observation to each category of maximum (minimum) postbaseline observation. Here categories may be low, normal, or high with cut-offs defined in the compound-level safety standards.	Safety
Listing of abnormal findings for laboratory analyte measurements, including qualitative measures	Safety

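### In this single-arm trial the hematology shift tables set the extreme of 2 pre-dose draws against the extreme of 3 treatment-period draws, so with no drug effect they lean towards worsening

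*SAP*

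**What the plan says.** SAP Section 5.13.6.2 plans, for eosinophils, a "Shift table summarizing the number and percentage of participants within each maximum baseline category versus each maximum postbaseline category" (Table KGBP.5.9), in addition to the standard laboratory summaries.

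Those standard summaries are in SAP Section 5.13.3, Table KGBP.5.6. A treatment-emergent high value means "patients shifting from a normal/low maximum baseline value to a high maximum postbaseline value", and low values mirror this with minima. The general shift table counts patients who "shift from each category of maximum (minimum) baseline observation to each category of maximum (minimum) postbaseline observation".

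SAP Section 5.1.2 fixes the baseline side: "the baseline period is defined as the time from the screening visit to the date/time of the first injection". For the treatment-emergent tables every result in that period counts: "Treatment-emergent abnormal laboratory and vital signs results: baseline will be all results recorded during the baseline period". Change-from-baseline summaries instead use one value, the last scheduled non-missing pre-dose assessment.

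The protocol's Schedule of Activities (Section 1.3) schedules hematology at Visits 1 and 2 (screening and baseline), Visits 4, 7 and 9 (Weeks 4, 16 and 24), early discontinuation and Visit 801. Clinical chemistry has the same schedule without Week 4.

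The SAP gives no postbaseline window for laboratory data. Section 5.13.2 names the treatment period for adverse events, and Table KGBP.5.8 does so for hepatic tests. The trial has one treatment group (Protocol Section 4.1).

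**The concern.** A maximum taken over more draws is on average higher, and a minimum lower. When the postbaseline side has more draws than the baseline side, a table of maximum against maximum leans upward and a table of minimum against minimum leans downward, with no change in the participants. In a randomised trial the control arm has the same schedule and shows how much lean to expect. Here there is none, and the natural reading is to compare the worsening cells with the improving cells, which is the comparison that the imbalance distorts.

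Eosinophilia is listed among the potential risks in Protocol Section 2.3, so the eosinophil table will be read closely. Under the minimum rule the same lean affects low counts.

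**Working it through.** The plan states no expected shift rate, so there is no figure to reproduce.

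**1. Draw counts (Schedule of Activities, Week 24 completer).**

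| | Pre-dose | Treatment period | With Visit 801 |
|---|---|---|---|
| Hematology | 2 | 3 | 4 |
| Clinical chemistry | 2 | 2 | 3 |

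**2. Direction, without a distribution.** If a participant's draws are exchangeable and continuous, the largest of *a* pre-dose and *b* postbaseline draws is equally likely to be any of them, so P(postbaseline maximum > baseline maximum) = b/(a+b). For 2 versus 3 this is 3/5 = 60%; for 2 versus 4 it is 4/6 = 67%; for equal numbers it is 50%. This shows the direction only, because the planned tables report category changes.

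**3. Category shifts.** Let q be a participant's probability that a single draw is normal. With no drug effect:

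- normal to high = E[q^a (1 − q^b)]
- high to normal = E[(1 − q^a) q^b]

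The expectation runs over participants, using a latent-normal model with p the overall share of draws above the limit and ICC the within-participant correlation. Both are assumptions.

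The upper end of the range (p = 30%, ICC = 0) can be checked by hand:

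- up = 0.7² × (1 − 0.7³) = 0.49 × 0.657 = 32.2%
- down = (1 − 0.7²) × 0.7³ = 0.51 × 0.343 = 17.5%
- net = 14.7 points; 0.147 × 95 = 14.0 participants; ratio 1.84

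Other cases for 2 versus 3 draws, by numerical integration:

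| p | ICC | Up | Down | Net (points) | Net of 95 | Ratio |
|---|---|---|---|---|---|---|
| 5% | 0.9 | 2.6% | 1.5% | 1.1 | 1.1 | 1.76 |
| 5% | 0 | 12.9% | 8.4% | 4.5 | 4.3 | 1.54 |
| 10% | 0.5 | 12.5% | 7.4% | 5.1 | 4.8 | 1.69 |
| 20% | 0.5 | 17.5% | 9.9% | 7.6 | 7.2 | 1.77 |

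A simulation of 1,000,000 participants at p = 20%, ICC = 0.5 also gave 17.5% and 9.9%. Over p 5-30% and ICC 0-0.9, the net excess is 1.1 to 14.7 points (about 1 to 14 of 95) and the ratio about 1.5 to 1.9. For 2 versus 4 draws the net is 2.0 to 25.0 points and the ratio 2.1 to 3.0. With equal draws (1 versus 1 or 2 versus 2) the net is 0.0 in every case.

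**4. A narrower set of assumptions, and how much is due to the imbalance.** Take log-scale between-person SD 0.6, within-person SD 0.30 or 0.45 (ICC = 0.36/0.45 = 0.80 or 0.36/0.5625 = 0.64), and 15% or 30% of draws above the limit. The last three columns give the treatment-emergent high rate among participants with no high value before dosing.

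| Within SD | p | Net of 95 (2 v 3) | Ratio (2 v 3) | 1 v 1 | 2 v 2 | 2 v 3 |
|---|---|---|---|---|---|---|
| 0.30 | 15% | 3.5 | 1.78 | 6.9% | 7.9% | 10.5% |
| 0.30 | 30% | 4.7 | 1.85 | 12.7% | 13.7% | 17.8% |
| 0.45 | 15% | 5.0 | 1.75 | 9.2% | 11.9% | 15.9% |
| 0.45 | 30% | 6.7 | 1.84 | 17.2% | 20.5% | 26.7% |

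The third draw adds 2.6, 4.1, 4.0 and 6.2 points in the four rows, or about 3 to 6. The rest of each rate is present with balanced draws.

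**The case against.** Several objections have force.

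- **Other displays exist.** Table KGBP.5.6 also plans by-visit box plots of observed values and of change from baseline, change to last observation, and a listing of abnormal findings. A reader can see from the box plots whether eosinophils rise at Weeks 4, 16 or 24 without this artefact. This stands, but these displays do not count participants who move between normal and high. A reader might also infer that Table KGBP.5.9 is the only eosinophil category display. It is not: Table KGBP.5.6 covers eosinophils too, although its treatment-emergent and shift tables follow the same rule.
- **Most treatment-emergent highs are not caused by the imbalance.** This stands. It would be wrong to attribute the whole 10-27% to it. Balanced 2-versus-2 draws give 8-21%, and one draw against one still gives 7-17%. Matching draw counts restores the balance between upward and downward shifts; it does not remove ordinary within-person variation.
- **The imbalance is not general.** Participants with data only to Week 16, as at the primary lock, have 2 versus 2. One who stops before Week 4 may have only 1 or 2 postbaseline draws. Continued Access participants skip Visit 801 (SAP Section 4.1).
- **It is tempting to call the problem specific to hematology.** That holds only if the window closes at the end of treatment. If Visit 801 counts, hematology is 2 versus 4 and chemistry is 2 versus 3. The SAP does not settle which.
- **Maximum-to-maximum is a useful screen.** It catches transient peaks, all analyses are descriptive, and the compound-level safety standards, which are not available here, hold the cut-offs. These are reasons to keep the tables, but they do not correct how the cells compare.

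**Conclusion.** The point holds as a minor improvement. For Week 24 completers the hematology shift and treatment-emergent tables compare 2 scheduled pre-dose draws with 3 treatment-period draws. With no drug effect and exchangeable draws, shifts towards abnormal outnumber shifts back by about 1.5-1.9 to 1. The net excess is about 3 to 7 of 95 participants under the narrower assumptions and about 1 to 14 over the wider range; these counts treat all 95 as completers. The imbalance contributes about 3 to 6 points to the treatment-emergent high rate among those eligible.

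The direction follows from the draw counts. The size rests on the share of draws near the limit and the within-person correlation, neither of which is in the documents. The planned 95 is the protocol's figure; the SAP still says about 80.

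A reader might infer that the plan cannot show whether eosinophils rise, or that 60% of participants will be tabulated as worse. The documents support neither. The by-visit displays are free of the artefact, and the 60% concerns one continuous maximum exceeding another, which no planned table reports.

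**What to change.** For eosinophils and the other hematology analytes, add category shift tables from the last pre-dose value to Week 4, to Week 16 and to Week 24 separately, showing both upward and downward shifts. With one draw on each side, the expected net shift under no effect is zero.

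Keep the maximum/minimum tables in Tables KGBP.5.6 and KGBP.5.9 as a screen for transient peaks. State that their laboratory postbaseline window is the treatment period, which leaves scheduled chemistry at 2 versus 2, and footnote the number of draws on each side.

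The cost is one extra table layout from data already collected. Single-visit shifts can miss a transient peak, which the retained tables still show.

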5.13.6.3. Infections, including herpes infections and relevant parasitic infections

Infections will be defined using the PTs from the MedDRA Infections and Infestations SOC. The MedDRA terms used to identify infections considered to be opportunistic infections (OI) in patients with immune-mediated inflammatory conditions treated with immunomodulatory drugs are based on Winthrop et al. (2015) and are listed in the compound-level safety standards. The list contains narrow (more specific) and broad (less specific) PTs with respect to these prospectively defined OIs. Definitions of herpes infections, parasitic infections, and skin infections are listed in the compound-level safety standards.

Table KGBP.5.10. Summary Tables/Listing Related to Infection Related Adverse Events

Summaries	Population
Summary of treatment-emergent infections by maximum severity	Safety
Summary of serious infections by PT	Safety
Summary of infection AEs resulting in permanent study drug discontinuation	Safety
Treatment-emergent adverse events - opportunistic and potential opportunistic infections	Safety
Treatment-emergent adverse events - herpes and parasitic infections	Safety
Treatment-emergent adverse events - skin infections	Safety
Treatment-emergent adverse events - infections characterization and follow-up form	Safety
Listing of patients with potential OIs, serious infections, herpes, and parasitic infections	Safety

Abbreviations: AE = adverse event; OI = opportunistic infections; PT = Preferred Term.

5.13.6.4. Conjunctivitis

Conjunctivitis events are events of special interest and will be identified using PTs nested within the categories of conjunctivitis and keratitis as described in the compound-level safety standards:

Table KGBP.5.11. Summary Table/Listing Related to Conjunctivitis

Summaries	Population
Summary of TEAE of conjunctivitis within categories	Safety
Treatment-emergent adverse events - conjunctivitis and eye inflammation characterization follow-up form	Safety
Listing of patients with conjunctivitis	Safety

Abbreviation: TEAE = treatment-emergent adverse event.

5.13.6.5. Hypersensitivity

Potential hypersensitivity reactions will be determined using the following SMQs: anaphylactic reaction, hypersensitivity, and angioedema. Potential hypersensitivity will be categorized as immediate (ie, occurring the same day as drug administration) and non-immediate (ie, occurring after the day of study drug administration but prior to subsequent drug administration). The planned summaries are provided in [Table KGBP.5.12](#).

Table KGBP.5.12. Summary Tables/Listing Related to Hypersensitivity

Summaries	Population
Treatment-emergent adverse events - potential immediate hypersensitivity reactions (events occurring on day of study drug administration)	Safety
Treatment-emergent adverse events - potential nonimmediate hypersensitivity reactions (events occurring after day of study drug administration)	Safety

5.1.1.1. 5.13.6.6. Injection Site Reactions (ISRs)

Injection site reactions are AEs localized to the immediate site of the administration of a drug. The evaluation of study drug related ISRs will be through the unsolicited reporting of ISR TEAEs. Injection site reactions will be defined using the MedDRA high-level term (HLT) of ISR, excluding certain PTs (eg, those PTs related to injections into a joint) and administration site reactions as described in the compound-level safety standards.

Table KGBP.5.13. Summary Tables Related to Injection Site Reactions

Summary	Population
Summary of TEAE of ISR overall, and by PT	Safety

Abbreviations: HLT = high-level term; ISR = injection site reaction; PT = Preferred Term; TEAE = treatment-emergent adverse event.

5.13.6.7. Malignancies

Malignancies will be defined using PTs from the Malignant tumors SMQ and summarized separately for the 2 categories: Non-melanoma skin cancer (NMSC) and malignancies excluding NMSC.

Table KGBP.5.14. Summary Tables Related to Malignancies

Summary	Population
Summary of TEAE of malignancies within categories of NMSC and malignancy excluding NMSC	Safety

Abbreviations: NMSC = non-melanoma skin cancer; TEAE = treatment-emergent adverse event.

5.13.6.8. Atopic Dermatitis Exacerbation

Atopic dermatitis exacerbation will be defined using PTs specified in the Compound Level Safety Standards and summarized for the Safety Population.

Table KGBP.5.15. Summary Tables Related to Atopic Dermatitis Exacerbation

Analysis	Population
Summary of TEAE of atopic dermatitis exacerbation	Safety

Abbreviations: TEAE = treatment-emergent adverse event.

5.13.6.9. Suicide/Self-Injury

The PTs from the suicide/self-injury SMQ [20000037] will be summarized.

Table KGBP.5.16. Summary Tables Related to Suicidal Ideation and Behavior

Analysis	Population
Summary of TEAE of suicide/self-injury	Safety

Abbreviations: TEAE = treatment-emergent adverse event.

5.14 Subgroup Analyses

Subgroup analyses will be conducted for the primary endpoint, EASI-75 at Week 16, using descriptive statistics.

The following subgroups will be analyzed:

- Baseline Severity
- Sex
- Age (≥ 12 to < 18 , ≥ 18)
- Race +/- ethnicity
- Fitzpatrick phototype

Some additional subgroup analyses may be added. The analysis of additional subgroups will not require an amendment to the SAP.

5.15 Protocol Deviations

Protocol deviations will be identified throughout the study. Important protocol deviations are defined as those deviations from the protocol likely to have a significant impact on the completeness, accuracy, and/or reliability of the study data or that may significantly affect a patient's rights, safety, or well-being.

Potential examples of important protocol deviations include patients who violated the inclusion/exclusion criteria, used an interfering concomitant medication, and significant non-compliance with study medication (<75% of expected injections). Refer to a separate document called "KGBP Trial Issues Management Plan" for the important protocol deviations with categorizations.

The number and percentage of patients having important protocol deviations will be summarized within category and subcategory of deviation for Weeks 0-16 of the Treatment Period using the ITT population and for Weeks 16-24 of the Treatment Period using Treatment Period II Population.

A by-patient listing of important protocol deviations will be provided for the ITT population.

5.16 Interim Analyses and Data Monitoring

Interim Analysis:

One interim analysis (primary lock) will be conducted after all enrolled participants have been evaluated at Week 16 or discontinued prior to Week 16. This interim database lock will include all efficacy and safety data collected by the cutoff date. Due to the open-label and descriptive nature of this study, there is no unblinding nor alpha adjustment.

Additional analyses and snapshots of study data may be performed to fulfill the need for regulatory interactions or publication purposes.

Final DBL: A final DBL will occur after all patients have either completed the study through the 12-week safety follow-up period of the study or discontinued the current study.

5.17 Annual Report Analyses

Based on regulatory requirements for the DSUR, reports will be produced (if not already available from the study CSR) for the reporting period covered by the DSUR.

5.18 Clinical Trial Registry Analyses

Additional analyses will be performed (if not already available from the study CSR) for the purpose of fulfilling the CTR requirements.

Analyses provided for the CTR requirements include the following:

Summary of AEs, provided as a dataset, will be converted to an XML file. Both SAEs and ‘other’ AEs are summarized by MedDRA PT.

- An AE is considered ‘serious’ whether or not it is a TEAE.
- An AE is considered in the ‘other’ category if it is both a TEAE and is not serious. For each SAE and ‘other’ AE, for each term the following are provided:
 - the number of participants at risk of an event
 - the number of participants who experienced each event term, and
 - the number of events experienced.
- Consistent with www.ClinicalTrials.gov requirements, ‘other’ AEs that occur in <5% of patients/subjects may not be included if a 5% threshold is chosen (5% is the minimum threshold).
- AE reporting is consistent with other document disclosures (eg, the CSR, manuscripts, and so forth).

Appendix 1. Definition of Rescue Medications

The AD rescue therapy in this study is defined as: high-potency TCS >10 days, topical JAK inhibitors, and systemic AD therapy. The topical and systemic treatments are defined as follows:

1. Topical AD Treatment (including TCSs, TCI, crisaborole, and Ruxolitinib)

Route of topical treatments includes: Topical and Transdermal.

TCS: ATC code is D07

High Potency TCS: ATC codes are D07AC or D07AD

Low or moderate potency TCS: ATC code is D07, excluding D07AC or D07AD

TCI: PT includes: TACROLIMUS, PIMECROLIMUS

Crisaborole: PT includes: CRISABOROLE

Topical Ruxolitinib: ATC code is D11AH09

2. Systemic AD Treatment (including systemic corticosteroids, immunosuppressant, biologics, and phototherapy/PUVA)

Route of systemic treatments administration includes: Oral, Intra-Arterial, Intramuscular, Intraperitoneal, Intravenous, Subcutaneous, and Transdermal. (This condition applies to the following categories except for phototherapies.)

Systemic Corticosteroids: ATC code is H02

Immunosuppressant: Defined as: ATC2 is L04 or PTs of Abrocitinib or Ruxolitinib excluding PTs mentioned in Biologics

Biologics: Defined as following PTs:

Infliximab, Infliximabum, Etanercept, Etanerceptum, Adalimumab, Adalimumabum, Certolizumab, Certolizumabum, Certolizumab pegol, Golimumab, Golimumabum, Ozoralizumab, Afelimomab, Afelimomabum, Tumor Necrosis Factor Alpha (TNF-) Inhibitors, Tabalumab, Tregalizumab, Anakinra, Basiliximab, Basiliximabum, Daclizumab, Daclizumabum, Tocilizumab, Tocilizumabum, Mepolizumab, Mepolizumabum, Rilonacept, Rilonaceptum, Ustekinumab, Canakinumab, Briakinumab, Fezakinumab, Sirukumab, Sarilumab, Lebrikizumab, Secukinumab, Olokizumab, Gevokizumab, Brodalumab, Ladarixin, Ixekizumab, Dupilumab, Tildrakizumab, Tildrakizumabum, Reslizumab, Reslizumabum, Guselkumab, Guselkumabum, Olamkicept, Fletikumab, Bimekizumab, Mirikizumab, Risankizumab, Abatacept, Ligelizumab, Vedolizumab, Belimumab, Nemolizumab, Tralokinumab, Omalizumab

Phototherapy or PUVA:

Programming search of medication name (actual term or PT) contains 'photo' then medicals to manually review to confirm whether the medication in question is indeed 'Phototherapy' or 'Photochemotherapy'.

PPD

PPD

23 Jun 2023 14:52:57 UTC (Z)

REASON: I approve this document

d5b66f2f-11e1-4ad9-8ea4-c216ad4f48c5

PPD

PPD

12 Jun 2023 15:29:11 UTC (Z)

REASON: I approve this document

7543fdb-1287-4fef-83c0-81a70287c57a

PPD

PPD

09 Jun 2023 20:08:20 UTC (Z)

